6.2 Procedures for Assessing Efficacy

Data collection will be the responsibility of the local clinical team led by the local PI and research personnel at each site. Data will be recorded in a standard Case Report Form (CRF), which will be provided by the CTU. Three participant identifiers (Participant ID allocated at enrolment, initials and age at enrolment) will be captured on the CRF.

Assessments will be performed according to the schedule in the study schema (p10). Overall responsibility for collating data from all centres will reside with the Trial Manager. All data will be pseudo anonymised with participants assigned a unique participant ID number at enrolment by the local research team, who will hold the key. A copy of the consent forms will also be filed in the participant's hospital notes, investigator site file and a copy will be given to the participant. Completed consent forms will not be sent to the CTU.

6.2.1 Procedures at enrolment

Enrolment will occur as soon as possible after screening and informed consent for entry into the study has been given. Background data (participant characteristics) will be collected and include; participant age, gender, heart rate and blood pressure, medical history to include ischaemic heart disease, hypertension, diabetes as well as current dialysis status (No dialysis, Peritoneal or Haemodialysis). Anticoagulants such as Aspirin, Clopidogrel, Dipyridamole, Warfarin or Non-Vitamin K Anticoagulants will also be noted. A vascular access history will also be necessary, which will include previous CVC insertions, and AVFs creation. It will also be important to know whether the patient has had a formal pre operative ultrasound scan. Operative details will include date of surgery and type of fistula (Radiocephalic, ulnabasilic, brachiocephalic or brachiobasilic).

6.2.2 Procedures during week 2

- Ultrasound assessment
- Flow characteristics as defined by scanning protocol
- Routine clinical examination (if applicable as per local policy)
- Recording of first detection of "at risk" fistula either by clinical examination or (US)
- Recording of time-point at which a fistula is no longer patent on US.
- Recording of the formation of a new AVF
- Recording of reported fistula thrombosis

6.2.3 Procedures at week 4

- Ultrasound assessment
- Flow characteristics as defined by scanning protocol
- Routine clinical examination (if applicable as per local policy)
- Recording of reported fistula thrombosis

6.2.4 Procedures at week 6

- Ultrasound assessment
- Flow characteristics as defined by scanning protocol
- Routine clinical examination (if applicable as per local policy)
- Recording of reported fistula thrombosis

6.2.5 Procedures at week 10

- Clinical assessment of fistula function
- Number of successful/unsuccessful dialysis visits within 10-week period
- Secondary fistula patency at week 10- defined as the interval from the time of access placement until access abandonment, thrombosis, or the time of patency measurement including surgical or endovascular interventions (including the formation of a proximal neo-anastamosis) in order to re-establish functionality in thrombosed access.
- Recording of first detection of "at risk" fistula either by clinical examination or (US)
- Recording of time-point at which a fistula is no longer patent on US.
- The number of fistula operations and radiological salvage interventions (number, nature and timing) reported up to week 10
- Flow characteristics as defined by scanning protocol
- Recording of the formation of a new AVF
- Recording of reported fistula thrombosis
- Recording number of days dialysed via a central venous catheter (CVC), and CVCrelated septic complications

6.3 Blinding of Assessments

The ultrasound findings will be blinded, i.e. not be relayed to the participant or to the participant's clinical team.

The only acceptable reasons for unblinding are:

The participating centres' local standard of care includes a scan, or a clinical need for a scan is identified. In which case the centre will have access to study scan data for that timepoint (but not the other study scans) to avoid unnecessary additional scans being scheduled.

Or

During a trial scan, the AVF is seen to be thrombosed, in which case this information would be shared with the clinical care team to enable appropriate care to continue. In such cases, no further study scans would be required. Clinical outcome data will still be collected at week 10.

Patients who discontinue the study early will not be replaced.

6.4 Study Closure

The study will be closed after the last 10-week appointment of the last recruited patient is completed, and all data have been received, cleaned and the database is locked. Once the study is closed, participating centres will be contacted, and may be visited, to ensure that all documentation is filed and ready for archive.

7. Safety reporting

This is an observational study using Doppler ultrasound, to which there are no known adverse reactions. No adverse event data will be collected in this study.

8. Quality Assurance and Control

Data will be managed in accordance with the NHS Blood and Transplant Clinical Trials Unit's Management Process Descriptions.

8.1 Risk Assessment

A risk assessment has been conducted which acknowledges the potential risks to the study. This section provides an overview of the Quality Assurance (QA) and Quality Control (QC) measures that will be put in place to ensure the study is performed and data generated and recorded in accordance with the principles of ICH GCP.

8.2 Central Monitoring at CTU

The CTU data managers will review all data received for errors and missing data points.

8.3 On-Site Monitoring

The frequency, type and intensity for routine monitoring and the requirements for "for cause" monitoring will be detailed in a separate study specific monitoring plan.

8.3.1 Direct access to patient records

Participating investigators should agree to allow study-related monitoring, including audits, ethics committee review and regulatory inspections by providing direct access to source data and documents as required. Patient consent must be obtained for this.

8.3.2 Confidentiality

The data will be handled in accordance with the principles of the UK Data Protection Act and any subsequent data protection legislation.

8.4 Auditing

In addition to potential GCP inspections or audits by the host R&D department, NHSBT CTU reserves the right to conduct site audits, either as part of its on-going audit programme, or in response to adverse observations during monitoring visits.

9. Statistical Considerations

9.1 Method of Generating Allocation Sequence

No randomisation is required.

9.2 Outcome Measures

See Section 5.

9.3 Sample size

We have estimated that 20% of fistulas fail early and that early ultrasound has a positive predictive value (number of true positives/number of predicted positives, PPV) of 72% for predicting non-maturation. To estimate this with $\pm 10\%$ precision (i.e. the 95% confidence interval is from 62% to 82%), 78 predicted failures are required. We estimate that US predicts failure in 25% of fistulas, therefore, 312 fistulas overall are required. Allowing for 10% dropout, 347 fistulas are required. We anticipate that two models to predict primary fistula patency will be required and therefore we will have two PPVs- one for wrist fistulas and one for elbow fistulas. Assuming a ratio of 50:50 for wrist to elbow fistulas, the precision confidence interval will be from 55.3% to 85.2%.

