The literature relating to the use of ultrasound surveillance to salvage failing arteriovenous fistula is however conflicting, and a consensus strategy has not been reached. This may reflect variations in: the type of surveillance adopted; the type of fistula under surveillance, and the precise ultrasound scanning method. Ultrasound can reliably identify fistulas that have successfully matured (15, 16), and although the precise ultrasonic characteristics that constitute a mature fistula continue to be debated (17), adoption of a surrogate ultrasound definition of maturity avoids exclusion of pre-dialysis patients from dialysis trials. We will adopt a similar approach for the current proposal. Few studies have attempted to use ultrasound to characterise early maturation, immediately after fistula creation, but those that do suggest that successful fistula maturation (3, 18). Fistula vein diameter may also increase rapidly (3). Thus, assessment at these earlier time points may be predictive of later values. In a study of 153 patients, Itoga et al. performed early duplex ultrasound on newly-formed fistulas (4-8 weeks after creation) (19). A flow limiting stenosis was detected in 40% of

patients, in whom 81% underwent subsequent radiological intervention. Assisted primary patency of the fistulas in this group (compared to the cohort without detectable ultrasound abnormality) was 83 vs 96% at six months and 64% vs 89% at one year. There was no control cohort (patients who did not undergo routine surveillance), but the assisted patency reported for the entire study population would appear to be better than generally reported following fistula creation. One randomised study to date (20) has evaluated routine early ultrasound surveillance (2, 4 and 8 weeks after fistula creation, 150 patients), and reported a 13.6% fistula failure / non-maturation rate in the surveillance group, compared to 25.4% in the control group in whom ultrasound was performed on the basis of a perceived clinical indication. This difference did not reach statistical significance, but notably, the study was powered for a 20% difference in maturation. Our proposed study is powered for a 10% difference, with a corresponding increase in numbers of enrolled patients.

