9.5.1 Analysis of primary and secondary outcomes

The primary fistula patency rate by week 10 will be calculated alongside an exact 95% confidence interval based on all participants enrolled. It will also be calculated based on participants whose fistulas did not fail early.

The secondary outcomes will be presented using descriptive summary statistics.

Mixed multivariable logistic regression will be used to model primary fistula patency by 10 weeks to develop a model, which can be used as a risk-score calculator in the phase 2 trial (not part of this protocol). Two models will be built, one for wrist fistulas and one for elbow fistulas. Measurements taken from the first scan performed at week 2 will be considered as parameters in the model initially and further parameters from either the second scan or the third scan will then be considered. The choice of second or third scan will be based on the best fitting parameters, as assessed by significance level. A random effect for patient will be included in the models to account for multiple scan data per participant. The aim will be to build parsimonious models, which contain the minimum number of measurements, required to effectively predict primary fistula patency. A receiver operating characteristic

(ROC) curve analysis of the developed risk scores will be used to assist decisions regarding an appropriate cut-off for an indicator for when intervention is required for both wrist and elbow fistulas. The PPV will be calculated alongside an exact 95% confidence interval for the chosen risk-score cut-off.

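### The ±10-point precision that sets the sample size is a normal-approximation figure for an overall PPV the protocol does not otherwise describe, and Section 1.2 claims a power this single cohort cannot have

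*Protocol*

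**What the plan says.** Section 9.3 takes an assumed PPV "of 72% for predicting non-maturation" and asks for ±10 points around it: "the 95% confidence interval is from 62% to 82%), 78 predicted failures are required". It then scales up: "We estimate that US predicts failure in 25% of fistulas, therefore, 312 fistulas overall are required", and "Allowing for 10% dropout, 347 fistulas are required". All of this concerns one PPV over all fistulas.

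The same paragraph goes on to expect two prediction models and hence two PPVs, one for wrist and one for elbow fistulas, and gives the consequence: "Assuming a ratio of 50:50 for wrist to elbow fistulas, the precision confidence interval will be from 55.3% to 85.2" per cent.

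Section 9.5.1 confirms a separate model for each site, with a cut-off to be decided for each, and fixes the interval method: "The PPV will be calculated alongside an exact 95% confidence interval for the chosen risk-score cut-off".

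Section 1.2, after describing an earlier randomised surveillance study, states: "Our proposed study is powered for a 10% difference, with a corresponding increase in numbers of enrolled patients". Against this, the Synopsis (interventions to be compared) says that no formal interventional comparison will be made, Section 1.4 limits this protocol to the observational phase 1, Section 9.1 says that no randomisation is needed, and Section 9.3 contains a precision calculation only.

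**The concern.** Three stated properties of the design do not match the design.

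- **Interval method.** The interval that fixes the number of predicted failures is not the kind that the analysis section prescribes. The two intervals in Section 9.3 also appear to come from different methods, with no label on either.
- **Estimand.** The ±10 points that drive N attach to an overall PPV. The PPVs the protocol commits to are site-specific, each resting on about half the predicted failures.
- **Power.** A study with no comparison cannot be powered for a difference.

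The PPV is the quantity the study is sized on, and Section 1.4 makes phase 2 depend on ultrasound proving effective at identifying at-risk fistulas. A reader who takes away ±10 points, or power for a 10% difference, would credit the study with more than its planned estimates deliver.

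**Working it through.** **Inputs.** From Section 9.3: PPV 0.72, target half-width 0.10, 95% confidence, 25% of fistulas predicted to fail, 10% dropout, 50:50 wrist to elbow. From Section 9.5.1: exact interval, taken here as Clopper-Pearson. The 20% early failure rate ("We have estimated that 20% of fistulas fail early") does not enter the precision formula.

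**1. Reproducing the stated size (Wald).**

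n = z² p(1 − p) / d² = 1.96² × 0.72 × 0.28 / 0.10² = 77.4, rounded up to 78.

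78 / 0.25 = 312. 312 / 0.9 = 346.7, rounded up to 347.

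The Wald interval at n = 78 is 62.0% to 82.0%. Every stated figure reproduces.

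**2. Which method produced each stated interval.** The Clopper-Pearson limits for x events in n are the 0.025 quantile of Beta(x, n − x + 1) and the 0.975 quantile of Beta(x + 1, n − x), with x = 0.72n.

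| n | x | Stated | Wald | Exact |
|---|---|---|---|---|
| 78 (overall) | 56.16 | 62% to 82% | 62.0% to 82.0% | 60.7% to 81.6% |
| 39 (per site) | 28.08 | 55.3% to 85.2% | 57.9% to 86.1% | 55.3% to 85.2% |

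The overall figure is Wald and the per-site figure is exact.

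**3. Size of the method gap at n = 78.**

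- Lower arm: 72 − 60.7 = 11.3 points. Upper arm: 81.6 − 72 = 9.6 points.
- Total width: 81.6 − 60.7 = 20.9 points, a half-width of 10.4 against the stated 10.0.
- With a whole-number count, 56/78, the exact interval is 60.5% to 81.4%.

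**4. What the exact method would need for the stated precision (for scale only).**

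- Half-width of at most 10 points: 85 predicted failures. 85 / 0.25 = 340; 340 / 0.9 = 377.8, so 378.
- Lower arm of at most 10 points: 98 predicted failures. 98 / 0.25 = 392; 392 / 0.9 = 435.6, so 436.

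**5. Precision of the PPVs the protocol commits to.** A 50:50 split gives 78 / 2 = 39 predicted failures per site. The exact interval of 55.3% to 85.2% has a half-width of 14.9 points. For scale, Wald ±10 points on each would take 2 × 78 = 156 predicted failures: 156 / 0.25 = 624; 624 / 0.9 = 693.3, so 694 fistulas, twice the planned number.

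**6. The power statement.** The protocol gives no significance level, power, comparator rate or groups for this phase, so the 10% difference in Section 1.2 cannot be derived or checked.

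**The case against.** The strongest reply is that nothing has been miscalculated. Sizing a precision study with a normal approximation and analysing it with an exact interval is ordinary practice, Section 9.3 does not call 62% to 82% exact, and uncertainty in the assumed 72%, 25% and 10% matters far more than 0.4 points of half-width. This stands, and it limits the interval-method point to a matter of labelling.

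A reader might infer that the wider site-specific precision is concealed. It is not: the same paragraph announces two PPVs and gives 55.3% to 85.2%. The designers evidently accepted that width, and whether they should have is a matter of judgement.

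A reader might also infer that a combined PPV will never be calculated. The protocol cannot show that. Section 9.5 is a brief summary that defers detail to a statistical analysis plan, which was not available here, and Section 9.5.1 refers to the PPV in the singular. What can be said is that this protocol commits to two PPVs and describes no combined one.

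Nor should a combined PPV displace the site-specific ones. It would depend on the wrist-to-elbow mix and describe neither risk score, so making it the headline would be a preference and not a correction.

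On Section 1.2, the sentence may have been carried over from the planned randomised phase 2. That is an inference, but it would explain the wording. No design figure depends on the sentence. It nevertheless speaks of the proposed study and its enrolment, and as a statement about this protocol it is wrong.

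**Conclusion.** The point holds as a mismatch between stated and actual properties of the design, of minor to moderate severity.

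- Under the prescribed method, 78 predicted failures give 60.7% to 81.6%, so the stated lower limit of 62% is missed by 1.3 points.
- N is driven by ±10 points on an overall PPV, while the two PPVs committed to have about ±15 points each, as Section 9.3 discloses.
- The power claim in Section 1.2 has no calculation or comparison behind it.

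The documents do not support the stronger reading that the sample size is wrong or that N must rise. The 78, 312 and 347 are right under the Wald formula, and the larger numbers in the working only show scale. Nor can the study be called underpowered: it has no arms, so no power figure applies. Section 1.4 sets no PPV threshold for moving to phase 2, so nothing shows that the shift in the lower limit would change that decision.

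The figures assume an observed PPV of 72%, exactly 78 predicted failures split equally between sites, and Clopper-Pearson as the exact method.

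**What to change.** Keep N at 347 and make three changes.

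1. **Section 9.3.** State that 78 predicted failures give an exact 95% interval of 60.7% to 81.6%, that this applies to the PPV over wrist and elbow fistulas combined, and that the planned wrist and elbow PPVs each have an exact interval of 55.3% to 85.2%.
2. **Section 9.5.1.** Add the combined PPV (all fistulas flagged by either site's model) with its exact interval, reported alongside the two site-specific PPVs and not in place of them.
3. **Section 1.2.** Replace the power sentence with a statement that this phase is sized for the precision of the PPV and makes no between-group comparison.

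The cost is a few lines of text and one extra tabulation. Recruitment, scanning and data collection are unaffected. The stated overall precision becomes slightly less favourable.

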9.4 Interim Monitoring and Analyses

The feasibility of recruitment will be assessed based on data between month 3 and month 9 of the recruitment period. Our stop-go criteria for expanding to complete the full first phase study will be: 1) stop if fewer than 80 patients have been recruited; (2) Recruit additional centres if between 80-120 patients have been recruited; (3) Continue the trial as planned if recruitment rates are as predicted.

9.5 Analysis Plan (Brief)

The analyses will be described in detail in a full Statistical Analysis Plan. This section summarises the main issues.

9.5.1 Analysis of primary and secondary outcomes

The primary fistula patency rate by week 10 will be calculated alongside an exact 95% confidence interval based on all participants enrolled. It will also be calculated based on participants whose fistulas did not fail early.

The secondary outcomes will be presented using descriptive summary statistics.

Mixed multivariable logistic regression will be used to model primary fistula patency by 10 weeks to develop a model, which can be used as a risk-score calculator in the phase 2 trial (not part of this protocol). Two models will be built, one for wrist fistulas and one for elbow fistulas. Measurements taken from the first scan performed at week 2 will be considered as parameters in the model initially and further parameters from either the second scan or the third scan will then be considered. The choice of second or third scan will be based on the best fitting parameters, as assessed by significance level. A random effect for patient will be included in the models to account for multiple scan data per participant. The aim will be to build parsimonious models, which contain the minimum number of measurements, required to effectively predict primary fistula patency. A receiver operating characteristic

(ROC) curve analysis of the developed risk scores will be used to assist decisions regarding an appropriate cut-off for an indicator for when intervention is required for both wrist and elbow fistulas. The PPV will be calculated alongside an exact 95% confidence interval for the chosen risk-score cut-off.

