3.3 Co-enrolment Guidelines

Participation in other studies would not exclude participation in the SONAR study. Coenrolment is possible upon agreement with the TMG.

4. Screening procedures and Consent and pre-enrolment investigations

It will be the responsibility of the local clinical team (which may include the local researcher(s)) to identify eligible patients scheduled to have a newly created AV fistula and invite them to participate. Potentially eligible participants will be screened against the inclusion and exclusion criteria, given study information verbally and be provided with the approved patient information sheet. They will have time to consider their involvement and ask any questions. If they wish to participate, they will be fully consented using the approved study consent form.

A screening log will be completed to record all potentially eligible patients considered for entry to the study.

A unique ID will be assigned for each participant enrolled, denoted by site code and sequential number e.g. XXX_001.

Some participants' fistulae will fail, and it is acceptable to re-enrol these participants with a different unique ID number, if they have another fistula created as per the inclusion/exclusion criteria.

There will be no mandatory pre-enrolment investigations.

5. Study Outcomes

5.1 **Primary Outcome Measure(s)**

1. Primary fistula patency by week 10 according to surrogate ultrasound parameters (wrist fistula: minimum venous diameter 4mm, with flow >400 mls/min; elbow fistula: minimum venous fistula diameter 5mm, with flow >500mls/min (3)).

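### Repeated scans do not justify a patient random effect in the week-10 patency model, and with one outcome per fistula its variance cannot in practice be estimated

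*Protocol*

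**What the plan says.** Four statements in the protocol bear on this point.

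- **Outcome (Section 5.1).** It is "Primary fistula patency by week 10 according to surrogate ultrasound parameters", which gives one binary value per fistula.
- **Model (Section 9.5.1).** "Mixed multivariable logistic regression will be used to model primary fistula patency by 10 weeks to develop a model". The result is meant to serve as the risk calculator for phase 2. "Two models will be built, one for wrist fistulas and one for elbow fistulas".
- **Role of the scans (Section 9.5.1).** "Measurements taken from the first scan performed at week 2 will be considered as parameters in the model initially"; measurements from the second or third scan are then considered as additions. The scans are therefore explanatory variables.
- **Random effect (Section 9.5.1).** "A random effect for patient will be included in the models to account for multiple scan data per participant".

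Section 4 adds that a patient whose fistula fails may come back with another one: "Some participants' fistulae will fail, and it is acceptable to re-enrol these participants with a different unique ID number". A person can therefore contribute more than one outcome. The expected number is not given.

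**The concern.** A random intercept models correlation between several outcomes from the same unit. Here the repeated quantity is the predictor. Each fistula has one outcome however many times it was scanned, so the stated reason does not support the term and the scans cannot identify its variance.

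The model is the main product that phase 1 hands to phase 2. If its variance parameter is settled by chance or by software defaults, the coefficients have no stable scale. A calculator that sets the random effect to zero for a new patient, which is an obvious default, would give wrong absolute risks. The one genuine source of repeated outcomes, the patient who re-enrols with a second fistula, is not the reason given. It would also be missed if the study ID were taken to define the patient.

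**Working it through.** **1. The plan's own figures (Section 9.3).** Inputs are PPV 72%, precision ±10 points, 25% predicted failures and 10% dropout.

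- 1.96² × 0.72 × 0.28 / 0.10² = 77.4, rounded up to 78
- 78 / 0.25 = 312
- 312 / 0.90 = 346.7, rounded up to 347
- Per model: 78 / 2 = 39 predicted failures and 0.72 × 39 = 28.08 events. The exact 95% interval is 55.3% to 85.2%.

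All of these reproduce, and none involves the random effect. At 50:50, each model has 312 / 2 = 156 fistulas.

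**2. Why one outcome per fistula does not identify the SD.** Write σ for the random-effect SD and xβ for the linear predictor. The data inform only the probability averaged over the random effect, which is close to expit(xβ / √(1 + 0.346σ²)). A larger σ is offset by a proportionally larger β. Only the small departure of the averaged curve from logistic shape carries information on σ.

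**3. Simulation, one row per fistula.** Each dataset has 156 fistulas and two correlated scan predictors. The assumed failure log-odds are −2.0 + 0.8x₁ + 1.2x₂, which gives about 20% failures. Effect sizes and correlation are assumptions, not protocol figures. The reference is ordinary logistic regression (SD 0). Log-likelihood and coefficient columns average 40 datasets; the others average 8.

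| SD fixed at | Log-likelihood change | Coefficient ratio | √(1+0.346·SD²) | Largest shift, population-averaged risk | Largest shift, risk at random effect zero | Overlap of top 25% | PPV change |
|---|---|---|---|---|---|---|---|
| 1 | +0.002 | 1.15 | 1.16 | 0.015 | 0.04 | 0.99 | 0 |
| 2 | −0.02 | 1.50 | 1.54 | 0.027 | 0.11 | 0.99 | 0 |
| 4 | −0.05 | 2.45 | 2.56 | 0.033 | 0.21 | 0.99 | −0.003 |

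The largest log-likelihood change in any single dataset was 1.37 (at SD 4), below the 3.84 / 2 = 1.92 needed to exclude a value at the 95% level. The mean AUC change was below 0.0001, and the linear predictors correlated at 0.998 or more with the ordinary model.

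**4. What happens when the SD is estimated.** In the 40 datasets, 45% of estimates were below 0.1 and the upper quartile lay at about the search bound of 54.6. In 60 further datasets with the SD capped at 6, the estimate was about zero in 45% and at the cap in 33%. Slopes were 1.0 to 4.0 times the ordinary ones, for a median log-likelihood gain of 0.07. Mean predicted patency with the random effect at zero exceeded the observed value by a median of 6 points and by up to 15.

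A separate run agrees. The log-likelihood was −61.26 at SD 0.01 and −61.34 at SD 8, while a slope rose from 0.58 to 2.62 and mean predicted patency overshot by 2 to 12 points.

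**5. One row per scan, outcome copied onto two rows (8 datasets).**

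| SD | 0.01 | 1 | 3 | 10 | 30 | 60 |
|---|---|---|---|---|---|---|
| Log-likelihood | −120.8 | −109.2 | −88.6 | −77.0 | −74.5 | −74.2 |
| Slope | 1.4 | 1.5 | 2.1 | 4.0 | 9.2 | 16.8 |

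Copied outcomes always agree within a fistula, and the model explains that by an ever larger variance. In this layout the fit diverges. The AUC stays at 0.800, but with a single slope it does so by construction.

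**The case against.** **The SAP may settle it.** Section 9.5 calls itself a summary and leaves detail to a SAP. That would answer an omission. This is a stated term with a stated reason, and the reason is wrong.

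**A reader might infer that the model will diverge.** The protocol does not support this as a general claim. Entering week-2 measurements and then adding those of a later scan reads most naturally as one row per fistula. The reference to multiple scan data may hint at one row per scan, but that layout is never stated.

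**A reader might infer that the risk scores, the cut-off and the PPV are worthless.** They are not. The ROC analysis and the planned step "The PPV will be calculated alongside an exact 95% confidence interval for the chosen risk-score cut-off" depend on ranking, which the table shows to be almost unchanged. A new patient's unknown random effect is common to all mixed models and can be averaged over; population-averaged risks then move by only about 0.03.

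**A reader might infer that repeat fistulas are invisible to the analysis.** That goes too far. Section 6.2 says the local research team holds the ID key, and Section 6.2.1 collects previous fistula creation, so linkage is possible though not specified. Re-enrolment even makes a person-level effect identifiable in principle. It would probably rest on few patients, though, and a failed wrist fistula followed by an elbow fistula falls into two different models.

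**A reader might add that there is no site term.** That is a separate matter which a SAP may cover. Any design effect would need an intraclass correlation that the protocol does not give.

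**Conclusion.** The sentence on the random effect is wrong as written: repeated scans neither justify the term nor identify its variance. With one row per fistula, the consequence is an arbitrary coefficient scale (a factor of about 1.15 to 2.45 for SD 1 to 4). Absolute risks are also miscalibrated if predictions set the random effect to zero, with largest shifts averaging 0.04, 0.11 and 0.21 at SD 1, 2 and 4. Discrimination, the PPV at a cut-off, the week-10 patency rate with its exact interval, and the sample size are essentially or wholly unaffected. Divergence is confined to the one-row-per-scan layout.

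This should be fixed before the model is fitted, but it does not threaten the study. The sizes rest on assumed effects and on 8 to 60 simulated datasets, so they are illustrative. The flat likelihood and the common rescaling of coefficients follow from the model's structure.

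**What to change.** In Section 9.5.1, and in the SAP if it repeats the term, delete the patient random effect and its reason. Specify ordinary logistic regression, optionally penalised, with one row per fistula. Enter the week-2 measurements and the week-4 or week-6 measurements as separate covariates.

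In Section 4, ask sites, which hold the key, to record the earlier study ID when a patient re-enrols. Where one person has more than one fistula in the same model, use person-clustered variance.

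The cost is analysis wording and one linkage field. Scan collection and the 78, 312 and 347 do not change. The linkage field is easiest to capture at the time of re-enrolment.
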